## PURPOSE AND OBJECTIVES

**Purpose:** The importance of the research and the potential knowledge to be gained should be explained in detail. Give background information.

The use of methamphetamine and other psychomotor stimulants is both pervasive and increasing in the United States. Between 2015 and 2019, the rate of overdose deaths involving psychomotor stimulants has increased 180% (Han et al., 2021). Currently, there are no Food and Drug Administration-approved medications for stimulant use disorder (StimUD) available due to small and inconsistent effects observed for the medications evaluated to date (Brandt et al., 2021). However, contingency management (CM), an empirically support treatment for substance use in which individuals earn positive reinforcers for adherence to verifiable behaviors, is a very efficacious strategy in reducing cocaine and methamphetamine use for individuals with StimUD (Bentley, et al 2021; Bolivar et al., 2021).

To date, the research supporting CM for treatment for individuals with StimUD has been primarily conducted in settings where individuals are presenting for treatment. Recruitment in these studies is typically characterized as targeted toward “treatment seeking” individuals. However, many substance users are not interested in treatment, but do see value in harm reduction activities, including syringe exchange, and the importance of these services has recently been acknowledged by US health leaders. In addition to an array of harm reduction services, there is evidence that some individuals receiving these services will enter treatment if that treatment is offered within the “low barrier” environment of the harm reduction facility. However, limited research has been conducted examining interest treatment services in syringe exchange programs (McMahan et al., 2020).

Syringe exchange is one of the most widely implemented harm reduction interventions for individuals who use drugs in the US. Individuals who are actively using drugs by injection are encouraged to visit a harm reduction site and get a supply of new syringes and be given information and other health services relevant for individuals who inject drugs (e.g., hepatitis and HIV testing). The population of individuals who use these services may be using opioids (heroin, prescription opioids, fentanyl) or stimulants (cocaine/methamphetamine) or any other drugs by injection. Participants receive information about available treatments for those individuals who desire to reduce/stop their drug use. In fact, at the Safe Recovery program, the site of the proposed project, there is a low barrier buprenorphine program for individuals who use opioids and would like to receive buprenorphine but who don’t want to enter a formal treatment program. At present there is no comparable treatment for those individuals who use stimulants. This proposed project is a first attempt to explore the interest in CM as a treatment for their stimulant use disorder.

The purpose of this study is to examine the potential utility of a CM intervention for individuals with

StimUD who already participate in a low-barrier community-based syringe exchange program. To our knowledge, this will be the first study to specifically assess the potential efficacy and acceptability of a CM intervention for psychomotor stimulant abstinence among individuals who participate in a syringe exchange program. In addition, this study seeks to examine intervention implementation in a natural setting with a community-based service provider who will be implementing the intervention within their clinic.

**References.** Include references to prior human or animal research and references that are relevant to the design and conduct of the study.

Bentzley, B. S., Han, S. S., Neuner, S., Humphreys, K., Kampman, K. M., & Halpern, C. H. (2021). Comparison of treatments for cocaine use disorder among adults: A systematic review and meta-analysis. *JAMA Network Open*, 4(5), e218049-e218049.

Bolívar, H. A., Klemperer, E. M., Coleman, S. R., DeSarno, M., Skelly, J. M., & Higgins, S. T. (2021). Contingency management for patients receiving medication for opioid use disorder: a systematic review and meta-analysis. *JAMA psychiatry*, 78(10), 1092-1102.  
<https://doi.org/10.1001/jamapsychiatry.2021.1969>

## METHODS AND PROCEDURES

**Study Design:** Describe the research design, including a description of any new methodology and its advantage over existing methodologies.

We are proposing a two condition, parallel groups, randomized control pilot study to evaluate the efficacy of a financial incentives intervention among individuals who use stimulants and take part in a community-based syringe exchange program. The study design will include recruiting service recipients who already participate in programs offered by the Safe Recovery at the Howard Center, a syringe exchange program located in Burlington, VT (i.e., a convenience sample). The experimental group will have the opportunity to earn financial incentives contingent on providing a negative urine sample for stimulants using a point-of-care test, which indicates abstinence from stimulant use, in addition to health education on the health risks of stimulant use and substance injection. The control group will receive health education on the health risks of stimulants use and injection. All participants will participate in their syringe exchange services as usual. We chose the health education as the control because participants across both conditions already receive the services provided by the syringe exchange program. Moreover, this control condition will help control for a potential type of between-groups variability. The treatment condition will last for 12 weeks. The primary outcome measure will be point-prevalence stimulant abstinence, which will be determined by percentage of negative urine samples for stimulants using a point-of-care test.

**Procedures:** Describe all procedures (sequentially) to which human participants will be subjected. Identify all procedures that are considered experimental and/or procedures performed exclusively for research purposes. Describe the types, frequency and duration of tests, study visits, interviews, questionnaires, etc.

**Note:** A clinical research protocol may involve interventions that are strictly experimental or it may involve some aspect of research (e.g., randomization among standard treatments for collection and analysis of routine clinical data for research purposes). It is important for this section to distinguish between interventions that are experimental and/or carried out for research purposes versus those procedures that are considered standard therapy. In addition, routine procedures performed solely for research purposes (e.g., additional diagnostic/follow-up tests) should be identified.

All study procedures are for research purposes only. This will be an experimental study conducted at Safe Recovery at the Howard Center. All study procedures will take place in a private, designated room at Safe Recovery. [name], our co-investigator and collaborator on the project, is the program manager at Safe Recovery who has authorized and set aside this room as research space to be used for this study. Individuals receiving services at the Howard Center Safe Recovery will be approached for participation by a center staff member; this particular staff member's primary role at the Howard Center is to assist with research. This staff member is listed as a study team member in UVMClick, has a UVM netid, and has completed CITI training. Potentially eligible participants will be asked when they come in for services if they would like to participate in a research study. The research assistant will complete each step in the consent process documentation form (listed in the additional materials). Prospective participants who consent to participate in the study will move on to the screening procedure next. Participants will also be provided with the "Resources Sheet" at the same time as the informed consent.

### **Screening**

Participants will be recruited primarily from Safe Recovery, a harm reduction facility located at the Howard

Center in Burlington, Vermont. Approximately 225 individuals per month attend Safe Recovery to exchange used syringes for new syringes. Staff at Safe Recovery estimate that approximately 25% of these individuals use cocaine and/or methamphetamine as the primary drug they inject. Individuals receiving services at Safe Recovery will be asked about interest in participation by the center research staff. Potentially eligible participants will be asked when they come in for services if they would like to participate in a research study. If interested, prospective participants will be invited to complete the intake assessment.

### **Intake Assessment**

All prospective participants will complete a formal assessment at intake; participants will receive \$25 for completing the assessment. The screening will take no more than 2 hours. Prior to completing the intake assessment, the prospective participant will read through and sign the consent form; the consent form will contain information about the intake assessment and its procedures, along with the study procedures. During the intake, questionnaires will be completed using pen and paper, then will be uploaded onto the computer and into a secure web platform, REDCap. The assessment battery will include questionnaires that assess the following six areas: (1) sociodemographic, (2) substance use history, (3) substance use follow-back, (4) substance craving, (5) demand for substances, and (6) decision making. The first 3 areas will be assessed using the WA state syringe exchange survey and Treatment Effectiveness Assessment. Substance craving will be assessed using the three-item craving scale. Demand for substances will be assessed using the simulated substance purchase task. Decision making will be assessed using the monetary choice questionnaire. For additional detail about each measure, see each respective questionnaire. Participants will receive \$25 for their time and participation in completing the intake assessment.

### **Intervention Conditions**

Participants will be randomly assigned to one of two intervention conditions. These sessions will be administered by one of the following study team members: Howard Center research assistants, UVM research assistants helping with the project, or Drs. [name] and [name].

**Health Education Condition.** The Health Education condition is based on a previous intervention used as a control in a number of other studies (Mooney et al, 2013). Sessions consist of an educational program addressing a variety of health, wellness, and lifestyle topics adapted from a previously implemented wellness manual. One education topic will be discussed each day. The 12 daily educational topics will include: (1) stress relief, (2) nutrition, (3) hepatitis prevention, (4) HIV prevention, (5) sleep hygiene, (6) health screening, (7) meditation, (8) home emergencies, (9) healthy relationships, (10) common medical problems of people who use drugs, (11) strategies to reduce anxiety, depression and other negative moods, and (12) self-defense. Participants in this condition will be scheduled for two clinic visits per week for 12 weeks. Thus, the health education on the 12 topics listed above will be provided in addition to the services provided to all individuals in the Howard Center Safe Recovery program. At one session each week, the individual will meet with a study team member listed above who will review a topic handout with the participant. We anticipate these sessions will take approximately 10-15 minutes.

**Health Education plus Incentives for Abstinence.** Participants in the experimental condition will have the opportunity to earn financial incentives for abstaining from stimulant use, in addition to receiving the same health education as the control condition. Monitoring of stimulant use will occur through twice-weekly urinalysis during the 12 weeks of the intervention. Specimens will be screened for stimulant use using a 10-panel point-of-care test taken at the center. The financial incentives will be contingent on negative samples for stimulants which include cocaine, methamphetamine, and amphetamine. The incentive amount will start at \$25 and increase for each subsequent stimulant-negative urine sample, up to \$65 per sample. Only tests where the display indicates negative samples will result in participants earning reinforcement. The incentive amount

for the first stimulant-negative sample will be \$25. Every subsequent negative sample will increase by \$2.50, with a maximum amount of \$65. Thus, the maximum amount a participant could earn if they provide a stimulant-negative sample for the entire 12 weeks is \$1,220. A reset will occur if a participant submits a stimulant-positive sample or has an un-excused absence. The next time the participant submits a stimulant-negative sample, the incentive amount will reset to the initial voucher value (i.e., \$25). A recovery of the pre-reset value will occur after the participant provides two consecutive stimulant-negative samples; that is, the participant will recover back to their previously earned incentive level instead of restarting the incentive escalation process. The implementation of the financial incentives will be completed by the study team member overseeing the session (e.g., Safe Recovery staff, UVM RA staff). Based on similar studies using financial incentives, we expect participants will earn approximately 40% to 50% of the maximum possible earnings (Heil et al. 2008; Higgins et al., 1996, 2020).

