### **Data Collection**

The primary dependent variable is stimulant-free urine samples; all samples will be assessed using point-of-care test conducted at the center. Urine specimens will be collected for all participants at least once weekly throughout the study. Urine specimens are disposed of following recording of the result, thus, no samples are stored. Participants in the health education condition will receive \$10 for providing each urine sample (2x per week). Urine samples will be collected for participants in the financial incentives condition twice weekly for all 12 weeks of the intervention for which they can earn the incentives stated above by providing a negative urine sample. Participants in both conditions will also complete the questionnaires for decision making, demand for substances, craving, and treatment effectiveness at three additional times after baseline, at weeks 4, 8, and 12. Data for the questionnaires will be completed using pen and paper, then will be uploaded onto the computer and into REDCap. All participants will be compensated \$10 per assessment independent of substance use status to ensure high compliance.

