All efforts will be made to maintain confidentiality. Assessments will be completed in a private room at Safe Recovery. Prospective participants who are eligible (i.e., participate in the Howard Center's syringe exchange program) will be approached by a study team member and asked about their potential interest in participating in the study. If interested, participants will then be provided with information about the study (via informed consent) and the study team member will review all steps on the consent process documentation sheet and answer any potential questions. If the participant consents to participate, then they will be asked to complete the following questionnaires. At intake, the Washington State syringe exchange health survey will be used to assess sociodemographic, substance use history, and substance use follow-back (McMahan et al., 2020). Demand for substances will be assessed using the simulated substance purchase task (Murphy et al., 2011). Decision making will be assessed using the Monetary Choice Questionnaire (Kirby et al., 1999). Substance craving will be assessed using the three-item craving scale (McHugh et al., 2021). The intake assessment will take no longer than 120 minutes and will occur once at the intake.

At weeks 4, 8 and 12 of the intervention, all participants will complete the Monetary Choice Questionnaire, three-item craving scale, and demand for substances using the simulated purchase task. Data for the questionnaires will be completed using pen and paper, then will be uploaded onto the computer and into REDCap. Each assessment will take no longer than 20 minutes.

All data will be coded by an assigned identification number, with the codes known only by the investigators on this project. Names will not be connected with any results. The security of the records will be maintained by keeping paper files in a locked file cabinet and by keeping REDcap computer files in password protected files. The master copy will be kept in a different locked file cabinet from the coded data. The results of this study will eventually be published, but patient confidentiality will be maintained.

**TYPES OF PROCEDURES** (Please do not use the "other" option unless the procedure is not listed.)

Check all that apply.

	Survey (mail, telephone, in-person, on-line)		Blood drawing:	Vol. 	Over days, weeks?		

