**Will the sponsor be conducting data monitoring visits for this study?**

Yes       No       NA

If yes, how often?

**Adverse Event, Unanticipated Problem (UAP), Reportable New Information (RNI):** Describe how events and UAPs will be evaluated and reported to the IRB. All protocols should specify that, in the absence of more stringent reporting requirements, the guidelines established in the "Adverse Event and Unanticipated Problems Reporting Policy" will be followed. The UVM/UVM Medical Center process for review of adverse events and UAPs to subjects or others should be included in the DSMP.

The primary investigators will evaluate all AEs, UAPs, and RNIs. We will follow the guidelines established by the Committees on Human Research "Adverse Event and Unanticipated Problems Reporting Policy". Any SAE will be brought to the attention of the PIs as soon as possible and no longer than 24 hours. Any AE or SAE that is both unexpected and related to study participation will be reported to the IRB within 7 days of the event. The IRB will make a determination as to whether additional reporting requirements are needed. IRB actions will be reported to the funding agency by the PIs no less than annually and more frequently as recommended by the local IRB. Any SAEs will be summarized in the yearly Progress Reports to the funding agency, including a review of frequency and severity. All SAEs will be followed through ongoing consultation with the physician caring for the patient until they resolve, result in death, or stabilize and are not expected to improve. The study staff will be in close contact with participants and health care providers throughout the study to monitor for potential unanticipated problems. Any unanticipated problems will be discussed at the weekly research staff meetings and reported as required to the CHRBSS using the Report of Protocol-Related Problems & Deviations Form.

**Withdrawal Procedures:** Define the precise criteria for withdrawing subjects from the study. Include a description of study requirements for when a subject withdraws him or herself from the study (if applicable).

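### The plan does not say how serious events are found, at visits or after missed visits, and plans no summary by arm, so they may be under-recorded, possibly unequally

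*Combined protocol and SAP*

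**What the plan says.** **Finding and reporting events.** The adverse event section under Data Safety and Monitoring states: "Any SAE will be brought to the attention of the PIs as soon as possible and no longer than 24 hours". On how events come to light it says: "The study staff will be in close contact with participants and health care providers throughout the study", with the aim of watching for unanticipated problems, which then go to weekly staff meetings. Data Safety and Monitoring adds continuing oversight of data and safety by the investigators and staff, without a form, question or interval. Events that are both unexpected and related go to the IRB within 7 days. Serious events are followed with the treating physician and summarised yearly for the funder by frequency and severity. Neither that summary nor Statistical Considerations mentions a breakdown of events by arm.

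**Scheduled contacts.** For the control arm, Intervention Conditions says: "Participants in this condition will be scheduled for two clinic visits per week for 12 weeks". The incentive arm gives urine twice weekly over the same 12 weeks. At intake, "the Washington State syringe exchange health survey will be used to assess sociodemographic, substance use history, and substance use follow-back", alongside measures of demand, decision making and craving. Later, "At weeks 4, 8 and 12 of the intervention, all participants will complete the Monetary Choice Questionnaire, three-item craving scale, and demand for substances"; Data Collection adds treatment effectiveness at the same weeks. An acceptability questionnaire follows at about week 12.

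**Missed visits.** Intervention Conditions states: "A reset will occur if a participant submits a stimulant-positive sample or has an un-excused absence". This applies to the incentive arm only, and what makes an absence excused is not defined. In the control arm a missed visit means only that the $10 sample payment is not earned.

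**The concern.** The Purpose section motivates the study with mortality: "the rate of overdose deaths involving psychomotor stimulants has increased 180"%. It also describes a service population that injects drugs and may use opioids. Overdose is nevertheless not in the Risks list, and no described contact asks about it.

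A participant who is admitted to hospital or dies does not attend. Missed visits are therefore where serious events are most likely to be found, and the plan attaches no enquiry to them. The one rule that calls for a judgement about why someone was absent applies in one arm only, which could make recording more complete there.

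Feasibility is part of Aim 1, and Statistical Considerations says the data are to inform a larger trial. How often serious events occurred, and why visits were missed, are outputs that the larger trial would need. If nobody asks at the time, analysts cannot reliably recover them later.

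**Working it through.** The plan gives no figure for event rates, missed visits or capture, so there is none to reproduce. The check has two parts.

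**1. What each described contact asks about**

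- Twice-weekly visits: a urine test, and at one visit a week a health education handout. No event question is described.
- Intake: the syringe exchange health survey, the Treatment Effectiveness Assessment, craving, purchase task and monetary choice. The items of the first two are not reproduced, so an event item there can be neither confirmed nor excluded.
- Weeks 4, 8 and 12: decision making, demand, craving and treatment effectiveness. No event question is described.
- About week 12: acceptability of the intervention.
- The procedures checklist ticks medical exams/history and observation, but no matching procedure is described.
- After a missed visit: no contact attempt and no recorded reason in either arm.

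The 24-hour rule, the 7-day IRB rule and the physician follow-up all start once an event is known. None of them finds it.

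**2. What this could mean with 40 participants**

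Inputs: 40 participants (Statistical Considerations); 1:1 allocation, so 20 per arm (assumed; the ratio is not stated); event and capture rates assumed over a range.

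*Is there likely to be anything to find?* The chance of at least one participant with an event is 1 − (1 − p)^40:

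- p = 2%: 55%
- p = 5%: 87%
- p = 10%: 99%

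*Effect of capture.* Expected recorded events per arm = 20 × p × capture.

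| True rate, both arms | Capture, control / incentive | Recorded, control / incentive |
|---|---|---|
| 10% (2 events each) | 50% / 50% | 1.0 / 1.0 |
| 10% (2 events each) | 50% / 90% | 1.0 / 1.8 |
| 20% (4 events each) | 50% / 50% | 2.0 / 2.0 |
| 20% (4 events each) | 50% / 90% | 2.0 / 3.6 |

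Equal under-capture understates the rate in both arms. Unequal capture creates a difference where none exists, in this direction against the incentives.

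*What complete capture could deliver.*

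- With 0 of 20 events, the two-sided 95% upper limit is 1 − 0.025^(1/20) = 16.8%.
- With no events in one arm, the two-sided Fisher p-value for k events in the other is 2 × C(20,k)/C(40,k). For k = 4 it is 2 × 4,845/91,390 = 0.106; for k = 5 it is 2 × 15,504/658,008 = 0.047. Five against none is the least that reaches p < 0.05.
- Exact Fisher power with 20 per arm is 7% for 5% against 15%, 17% for 5% against 20%, and 24% for 10% against 30%.

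Better capture therefore buys an even-handed description, not a test.

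**The case against.** The strongest reply is that a safety route exists and is proportionate. Staff and investigators monitor continuously, are in touch with participants and providers, and discuss problems weekly. Both arms share a twice-weekly schedule, and participants also attend for syringe services. No investigational drug is used, and the protocol template allows a simple investigator-run monitoring plan for minimal-risk studies, although this study is not declared minimal risk in the text shown. The review-frequency tick marks did not survive extraction, so the yearly funder summary is not shown to be the only periodic review. All of this stands. It means that capture is unstructured, not absent.

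A reader might infer more than the documents support:

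- *That no visit asks about events.* Two instruments are not reproduced. The most that can be said is that none is described as asking.
- *That events will be missed.* The monitoring text describes a way in which some would be noticed. The supportable word is may.
- *That an overdose or admission leads to a reset.* The reset is for un-excused absences, and nothing says how such an absence would be classed.
- *That the arms cannot be compared.* Allocation is known, so recorded events could be tabulated by arm. The comparison is unplanned and would rest on uneven information.
- *That capture will differ by arm.* No document says that staff ask for reasons in one arm only. The reset rule makes it plausible, no more.
- *That the number of visits missed without safety contact can be counted.* No missed-visit rate is given, and the expected 40% to 50% of maximum earnings does not separate positive samples from absences.

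What the reply does not supply is any stated step by which an event is first found, any follow-up of a missed visit, or any summary by arm.

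**Conclusion.** The point holds in limited form. The plan relies on unstructured contact to find adverse events, describes no event question at any visit, describes no contact attempt or recorded reason after a missed visit in either arm, and plans no safety summary by arm. Serious events may therefore be under-recorded, possibly unequally.

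The size cannot be fixed from the documents. The 2.0 against 3.6 illustration rests on assumed 1:1 allocation, an assumed 20% event rate and assumed capture of 50% and 90%; with equal capture the false difference disappears. The primary abstinence analysis is not in question. This is an inexpensive improvement that should be made before enrolment, because the information cannot be reliably rebuilt afterwards.

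**What to change.** Make three changes, the first two identical in both arms:

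1. In Data Collection, add one standard question at each scheduled visit about overdose, emergency care and hospital admission since the last visit. On the twice-weekly schedule this is 2 × 12 = 24 occasions per participant.
2. After any missed visit, have existing staff make one contact attempt and record the reason on the same form in both arms. In the incentive arm this record also documents the basis for calling an absence excused or un-excused. If contact details and permission are not already collected (the consent pages are not available to this review), add them at intake.
3. In the adverse event section and Statistical Considerations, plan a descriptive table of adverse and serious adverse events by arm, and state that 40 participants cannot test a difference.

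The adverse event section should then name the question and the missed-visit contact as the means by which events are found.

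The cost is one form item, brief contact attempts and one table. The downside is modest staff time and additional sensitive data to protect, for which the existing coding, locked storage and Certificate of Confidentiality already provide a framework.
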